Boost treatments can be delivered through a variety of techniques(9, 10) including a single electron field (used for superficial tumor beds) or multiple photon fields (2 or 3 fields typically) for tumors that are deep to the skin (usually > 3 cm). With the use of CT simulation to guide the delivery of the boost, the need for deep TB coverage has become more apparent and now most patients receive photons for the boost portion of their therapy because the use of electrons often misses part of the tumor bed (figure 1a). However, when photon beams are used, in comparison to electrons, more generous margins posterior to the surgical cavity are required to account for daily set up error and respiratory motion which is not necessary for a single en face electron field. Furthermore, there are only limited directions along which the radiation can be directed to the TB, and as a result, large volumes of normal breast tissue receive a substantial fraction of the prescription dose (figure 1b) which can lead to internal scarring (fibrosis) and poor cosmesis(8, 11, 12). The largest clinical series evaluating this issue demonstrated increased fibrosis and worse cosmetic outcome using photons(13). The clinical target volume for the boost is the TB, while an additional 1-1.5 cm margin of normal breast tissue is added isocentrically to account for daily set-up error and respiratory motion to define a planning target volume. Typically the boost is delivered after the whole breast portion of treatment, however, in various cases this sequence can be changed. For example, if significant skin breakdown occurs during the whole breast radiation phase, investigators can stop the whole breast radiation therapy and change to deliver dose only to the TB while allowing time for the rest of the breast to heal. This allows a continuous course of therapy to the highest risk of subclinical disease (i.e. the tumor bed).

Hypofractionation, or delivery of greater than standard 1.8 - 2 Gy fraction sizes per day, is a method of shortening overall treatment time in breast cancer. Historically, standard fraction sizes of 1.8-2.0 Gy for whole breast irradiation (WBI) were based primarily on studies examining squamous cell cancers from cervix and head and neck regions. The smaller fraction sizes exploited a biological differential in squamous cell cancer fractionation sensitivity versus normal

tissue fractionation sensitivity. This allowed relative sparing of surrounding normal tissue from low dose per fraction. However, investigators from the United Kingdom hypothesized that the fractionation sensitivity for adenocarcinoma of the breast is close to that of the normal breast tissue. Therefore, with increasing fraction size a sufficiently large reduction of total dose could be implemented to keep late toxicity constant without reducing the probability of tumor control[14,15].

In 2010, the Ontario Clinical Oncology Group published updated findings from a randomized trial with 12-year median follow-up showing that a 3-week hypofractionated WBI schedule yielded similar cancer control and breast cosmetic outcomes to a 5-week conventional WBI schedule[16,17]. These findings reinforced the body of evidence supporting shorter radiation treatment schedules from three prior randomized trials (the United Kingdom's Standardization of Breast Radiotherapy (START-A and START-B) and the Royal Marsden Hospital/Gloucester Oncology Center trials)[18-21].

In 2011, the American Society for Radiation Oncology practice guidelines endorsed hypofractionated WBI as “equally effective for in-breast tumor control and comparable in long-term side effects” with conventional whole breast radiation for patients with early-stage breast cancer who were (1) over age 50, (2) pathologic stage T1 or T2N0, (3) chemotherapy naive, and (4) radiation dose heterogeneity higher or lower than 7% of prescription dose[22]. The guidelines also permitted hypofractionated radiation for other patients with early-stage breast cancer, stating that “this guideline should not be interpreted to prohibit or oppose the use of hypofractionated whole breast radiation for patients not meeting all the criteria”. In 2013, the Choosing Wisely initiative, aimed at reducing health care costs, encouraged physicians and patients undergoing breast conservation therapy to discuss the duration of whole breast radiotherapy[23].

In our clinic, the utilization of hypofractionated radiotherapy has increased substantially especially since the NCI sponsored co-operative group trial RTOG 10-05 has closed (February 2014), which was a prospective phase III trial testing hypofractionation using a more sophisticated radiation therapy approach. Conventional fractionation is generally offered to patients with high grade tumors (ER/PR/Her2-neu negative AND any ER/PR status with Her 2 neu positive) and patients whose anatomy dictates a radiation dose heterogeneity.

[figure not shown]

Figure 1. (A) A typical treatment plan using superficial electrons that would under dose the deep portion of the TB (outline in red) which was estimated clinically prior to the common use of CT scans. (B) Photon plans are more commonly used as the target is shown to be deep, but requires a more generous margin posteriorly due to respiratory motion which is not an issue with en face electron fields. This unfortunately delivers more moderate and high dose radiation to the surrounding normal breast and potentially to the normal lung as well.

1.1. Innovative methods to deliver radiation to the tumor bed

Over the last decade, several more sophisticated approaches(24-28) have been developed to deliver radiation to just a part of the breast including brachytherapy (i.e. Mammosite™) and various intraoperative approaches using either electron beam or low energy x-rays to deliver a single dose in the operating room. These techniques were developed to treat select patients with partial breast irradiation, but initially were tested in combination with whole breast radiation to deliver the additional radiotherapy to the TB through the novel approach. One of the recent methods is named targeted intraoperative radiotherapy (TARGIT)(29). TARGIT utilizes low energy photons intraoperatively to deliver radiotherapy to the tumor bed immediately after the surgical excision of the tumor (prior to being awakened from anesthesia). Radiation therapy is delivered with a single delivery of 20Gy prescribed to the surface of the excision cavity with a rapid dose falloff where tissue 1 cm deep from the surface of the excision cavity receives between 5 to 7Gy. After the dose is delivered, the device is removed and surgical closure is completed. One of the major downsides to this intraoperative approach is that the surgical margins cannot be assessed at the time of surgery; subsequently 15-20% were found to have adverse histologic features requiring the addition of whole breast radiation(29). Patients who received whole breast radiation received 45-50Gy in 25 fractions. When this approach was initially tested, whole breast radiation was always delivered *following* the boost. Based on the largest series with long term follow up (median follow-

up of 60.5 months), the 5-year local recurrence rate was less than 2%(30). Similarly, investigators have used intraoperative electrons prior to whole breast radiation. Long-term local control rates and cosmesis appear similar to or better than more conventional techniques. Doses of 9 to 10 Gy in a single treatment in the operating room were delivered typically using 9 MeV electrons prescribed to the 90% isodose line. Lemanski(31) et. al. described no grade 3 side effects in 50 patients treated with this approach, but did have a 12% risk of grade 2 subcutaneous fibrosis which is similar to large series using conventional boost techniques²⁶. In Europe, based on short follow up, there has not been a difference in local control or cosmesis between intraoperative radiotherapy and conventional electrons from EORTC 22881/10882(8).

All of the these treatment techniques described above have the down side of being invasive (i.e. brachytherapy) requiring a second procedure to place the device prior to treatment or lengthening the time under anesthesia (i.e. intraoperative radiation) by at least 30 – 60 minutes. Additionally due to these factors, sophisticated dosimetric evaluation ensuring appropriate dose coverage cannot be performed due to a variety of technique and logistical factors.

Faculty members at the University of Maryland, Baltimore invented a method and device for delivering stereotactic radiotherapy specifically for breast cancer(32). By licensing the technology from University of Maryland and collaborating with the PI and his research team, Xcision Medical Systems, LLC has developed a new breast specific stereotactic radiotherapy machine, the GammaPodTM, with the support of an NIH SBIR grant. Based on stereotactic radiosurgery principles, this new device is capable of delivering focused radiation to the target while sparing the surrounding normal tissues and structures(32, 33). The advantages include: (1) it is completely non-invasive in comparison to other technologies (i.e. MammositeTM or equivalent devices) currently used for high dose radiation delivery to the breast as described above, (2) the vacuum assisted breast immobilization device has been designed to have improved accuracy and reproducibility, allowing a reduction in the set-up error to less than 3 mm(34). The initial breast immobilization device was tested on an in-house protocol (GCC0727) at the Marlene and Stewart Greenebaum Cancer Center, where the accuracy and comfort was demonstrated although a substantial percentage of the breast immobilization devices became dislodged requiring improvements. A new version of the breast immobilization device was designed and is now being tested on GCC1047 confirming its accuracy and reproducibility. This study is ongoing and data have been used to validate the planned treatment margins for the proposed study GCC1202. Based on the 12 patients for whom data has been analyzed, the reproducibility of target position within the cup remains <3 mm. The patient is treated in the prone position, similar to positioning for stereotactic breast biopsy or MR imaging of the breast, thus minimizing the effect of breathing motion. In deciding on a treatment margin to account for overall positional uncertainty, mechanical accuracy of the patient couch (relative to the beam isocenter) must be taken into account in addition to the accuracy of target positioning within the cup. We have conservatively added another 2 mm to the margin to account for couch uncertainties. This is based on a measured couch position

uncertainty within 1 mm. Subsequently, we propose to use a setup margin of 5 mm. (4) This device uses 36 non-coplanar 60Co sources that rotate during treatment to form 36 non-coplanar arcs, producing a dose distribution similar to that of the Gamma Knife™ for intracranial targets which is substantially more conformal than the 3 field approach which is a standard practice for TB boost (see figure 1B).

This study proposes to proceed to a 1st in human clinical feasibility study by delivering a single moderate dose to the TB using the GammaPod™ on a day shortly before whole breast radiotherapy. The FDA has requested this clinical demonstration of the device with an IDE prior to obtaining FDA marketing clearance via the 510k mechanism. The goal of the study, as proposed by the FDA, was to demonstrate that a treatment could be delivered. The clinical trial protocol for phantom studies to validate the device's accuracy has been discussed with the FDA. Therefore, the primary end point of this study is simply feasibility and patient safety. We will also evaluate overall patient comfort and dosimetric accuracy through patient-specific phantom measurements conducted before the treatment delivery.

1.2. Study rationale

In this study, we plan to deliver a 8 Gy TB boost using the GammaPod™ system followed by a conventional (50Gy in 25 fractions) or hypofractionated (40Gy in 15 fractions) course of whole breast radiation. The clinical target volume receiving 8 Gy will be the surgical cavity as defined by the surgical clips and post-surgical changes + 5 mm. The planning target volume will add 5 mm to the clinical target volume to account for geometric uncertainties. The current standard of care in our clinic when delivering a conventional course of whole breast radiation is to deliver between 60 and 66 Gy to the tumor bed when negative margins are achieved, with the initial ~45-50Gy delivered to the whole breast and the 10-16Gy TB boost delivered in 5-8 fractions. The current standard of care in our clinic when delivering a hypofractionated course of whole breast radiation is to deliver between 50 and 52 Gy to the tumor bed when negative margins are achieved, with the initial ~40-42.5Gy delivered to the whole breast in 15 or 16 fractions respectively followed 10Gy TB boost delivered in 4 or 5 fractions (total 20). The clinical target volume for the TB boost in this study is quite similar to conventional TB boost. The only difference is that the PTV margin is smaller in this study (5mm instead of 10mm) due to the reduced set up uncertainties with the breast cup immobilization and localization devices. The current institutional standard is covering the TB + 15 mm dosimetric margin. Since our reproducibility is improved by 5 mm with the aid of the breast immobilization cup, the TB + 10 mm dosimetric margin will be used on this study. Using the radiobiological equivalent dose (BED) formula, $\{BED = nD(1 + D/(\alpha/\beta))\}$, the 8 Gy single fraction dose is equivalent to 16 Gy delivered in 8 fractions. Wherein the BED formula, n is the number of fractions, D is the dose per fraction and α/β is estimated to be between 3 and 4(35). On this study, we will deliver either 40 Gy in fifteen (15) fractions (hypofractionated) or 50Gy in twenty-five (25) fractions (conventional) to the whole breast following a single 8 Gy boost using

the GammaPod. The summed dose to the boost region will be radiobiologically equivalent to a total dose of 52 (hypofractionated) or 66Gy (conventional).

The safety and feasibility of delivering the boost dose to the tumor bed using a single fraction external beam is supported by past clinical trials. Besides the use of electrons and external beam from a linear accelerator, intracavitary balloons and intraoperative x-rays and electron beams have also been used to deliver a TB boost. In the TARGIT trial, a single dose of 20Gy is delivered to the TB using the Intrabeam™ device while the dose drops to between 5 and 7 Gy 1 cm into the normal breast. With long term follow up (median follow-up of 60.5 months), the 5-year local recurrence rate was less than 2 %(20). In the largest intraoperative electron experience, investigators *delivered 9 to 10 Gy in a single treatment prior* to whole breast radiation using 9 MeV electrons(31). Long-term local control rates and cosmesis appear similar to or better than more conventional techniques (36). In this proposed study, we plan to deliver 8Gy to the TB rather than 20Gy with low energy x-rays or 9-10 Gy with electrons before whole breast irradiation, based on 1) there is no benefit of dose escalation over the biological equivalent dose of 16 Gy at 2 Gy per fraction(26) which is equal to 8 Gy in 1 fraction and 2) known increased side effects with higher doses to the tumor bed(8, 36). We believe that the proposed dose should be similarly tolerated as observed in these trials, since the volume of normal breast irradiated is similar using a lower dose. In addition, this treatment will similarly shorten treatment by 1 to 1 ½ weeks by replacing the 8 treatments to the TB.

1.3. Schema/procedure

The general treatment sequence is shown in the flow chart below. After lumpectomy and sentinel node biopsy, the patient may or may not be recommended for adjuvant chemotherapy. If chemotherapy is recommended, radiation therapy will start within 6-8 weeks from completion of chemotherapy. If chemotherapy is not recommended or performed prior to surgery, radiation therapy will start within 6-8 weeks following surgery. Rather than delivering the tumor bed boost at the end of the whole breast radiation, we will deliver the tumor bed boost dose of 8 Gy in a single treatment using the GammaPod before whole breast radiation. The clinical target volume for the single treatment is the tumor bed (defined as the surgical cavity including surgical clips and any surgical changes) plus a 5 mm uniform margin. A further 5 mm uniform expansion in all directions will be added to the clinical target volume to make the planning target volume. This 5 mm margin is based on our setup reproducibility study with the current patient loader and breast cup system (GCC1047), as well as conservatively taking into account mechanical uncertainty of couch positioning. Twelve patients have contributed data to the setup reproducibility analysis (see the Pre-Clinical Tests section, Tab 3). The reproducibility of target location within the cup to within two standard deviations of the mean (95% confidence limit) has been found to be 2.9 mm.

After the single fraction GammaPod treatment, standard whole breast radiation therapy delivering 50 Gy in 25 treatments or 40 Gy in 15 treatments will be administered.

Patients will first be simulated in the supine or prone position in preparation for whole breast radiation without the breast immobilization device. If the surgical cavity is clearly visible and the TB volume is less than 25% of the whole breast volume, the patient will be a candidate for single fraction GammaPod boost (this study) and considered for treatment on study. The patients will be approached after the simulation and offered the study if they otherwise meet the eligibility criteria. Otherwise, patients will be off the study and be treated with the standard of care, i.e, start with 25 fractions of whole breast irradiation followed with 5-8 fractions of TB boost. If patients agree for treatment on study and sign informed consent, they will be set up to undergo a second CT simulation in the prone position with the vacuum-assisted breast immobilization device in place followed by the TB boost treatment using the GammaPod system on a day prior to whole breast irradiation (more details below).

For delivering the tumor bed boost dose with the GammaPod, the patient will first be fitted with the breast immobilization cup using silicone inserts and silicone adhesives as necessary to obtain an adequate seal. The negative pressure applied on the cup will be set to -150mmHg based on experience from our setup reproducibility studies using earlier and current versions of the cup system (IRB approved studies GCC0727 and GCC1047 respectively). In GCC0727, pressure settings between -100 mmHg and -175 mmHg were tried, with -150 mmHg being used most commonly. In GCC1047, a pressure of -150 mmHg has been consistently used for all patients, and found to be well tolerated and effective. Consequently, we have decided to use this value for all patients in the proposed clinical use study GCC1202. For context, a typical breast pump for a nursing female generates a peak pressure of about -250 mmHg. Once the negative pressure is established on the breast tissue, the patient will receive a CT scan wearing the vacuum-assisted breast cup that locks onto the GammaPod imaging table. The breast cup and imaging table is show in Figure 2 below. Note the pink silicone flange on the cup to provide a seal onto the patient's chest. The imaging table allows the affected breast with the breast cup on to be locked into the opening of the table surface while the patient is in the upright position. The step of the table is adjustable, so that patients of different heights can have their affected breast placed through the opening on the table. The treatment table has the same surface shape, step adjustment, and rotating mechanism as the imaging table to ensure that imaging and treatment have the same patient setup geometry.

Figure 2. a) The revised breast cup assembly and b) the patient imaging couch that rotates from near vertical to horizontal for imaging and treatment c)

Regarding ensuring that adequate pressure is maintained throughout the procedure, there are multiple safeguards as outlined here:

- (i) During the period that the patient is not being scanned or treated, a therapist will be accompanying the patient and monitoring the pump's pressure gauge. In addition to the gauge there is an LED light that indicates a current drop in pressure to below -100 mmHg and also a "latch" LED that comes on when a drop in pressure occurs and stays lit even if pressure is restored. The conservative value of -100 mmHg was chosen as an alert and interlock (see iii below) threshold with the rationale that a value within the range observed to fully immobilize the skin of the breast provided optimum patient safety. **At any time after CT scanning and prior to treatment, if on examination of the latch LED a pressure drop to below -100 mmHg has occurred, the procedure will be halted and the physician will order a repeated imaging study and if already planned the patient will be re-planned.**
- (ii) During CT scanning, the pressure gauge and indicator lights will be visible via the CT room's video camera. Scanning can be halted in the event of a pressure loss.
- (iii) During GammaPod treatment, in addition to video monitoring, a pressure monitoring cable from the pump provides an interlock that shuts off the radiation in the event of a pressure drop below -100 mmHg.

It should be noted that the pump is continually on throughout the procedure and can maintain pressure even in the event of small air leaks in the seal between the flange and skin. While the patient is lying prone for scanning or treatment, their weight further reinforces the seal between the cup flange and chest. The routine use of a biocompatible medical adhesive (Hollister 7730

Medical Adhesive Spray, as used for an ostomy – see Figure 3 of Pre-Clinical Tests Section, Tab 3) further helps to establish and maintain a good seal. During the reproducibility studies, significant pressure loss has never been observed during CT scanning while the patient was lying prone in the treatment position. A photograph of the pump, with pressure gauge indicating -150 mmHg is shown in Figure 4 of the Pre-Clinical Tests Section. During treatment, a cable from the pump enables interlocking of the radiation delivery in the event of a preset pressure drop (to -100 mmHg).

Both the CT simulator and the GammaPod unit are within the Department of Radiation Oncology. A typical breast CT simulation takes 10-15 minutes. After the CT scan, the images will be transferred to the treatment planning system, which is specifically designed by Xcision for the GammaPod system. It uses inverse planning principles to optimize a dynamic path of the focal spot to paint the prescribed dose distribution. On the treatment planning system, the target volume will be delineated by the prescribing physician. They can also delineate critical organs and structures and set a dose limit to them. The typical time required for target delineation is 10-15 minutes. After target delineation, a GammaPod treatment plan will be optimized based on the dose prescriptions and dose limitations. Plan optimization takes less than 2 minutes including the final dose calculation.

The treatment plan will be reviewed and approved by the prescribing physician and physicist before being sent to the GammaPod system for delivery. For a plan to be acceptable, the 8Gy isodose line must cover 95% of the PTV (tumor bed plus 10 mm margin), and must be at least 5mm from the breast skin surface. The minimum PTV dose must be greater than 7.2Gy, i.e., a maximum of 10% cold spot is allowed if 95% of PTV is getting 8Gy or more. The maximum PTV dose must be less than 9.6Gy, i.e., a maximum of 20% hot spot is allowed. For the boost PTV, these dose uniformity measures are significantly less as compared to other boost techniques such as MammoSite or Intrabeam, where the hot spot can be over 100% greater than the prescribed dose and encompasses the entire surgical cavity, and has not been associated with poor cosmetic results(29, 37-39).

As the treatment plan is being developed, the patient will be escorted or transported to the GammaPod treatment room with the breast cup in place and the vacuum seal maintained. After the treatment plan is transferred to the GammaPod control console, the patient will then be set up on the treatment table in the same geometry and manner as for CT imaging. The optimized treatment plan will then be delivered by the GammaPod system. For a spherical target size of 5 cm in diameter, the treatment would take about 12 minutes. For a 3 cm target, the treatment time is less than 3 minutes. We expect that the total time from wearing the breast cup for CT simulation to the completion of treatment is less than 75 minutes.

At the conclusion of the treatment, the patients will be asked about the comfort of the cup system and procedure, and their skin will be checked for any signs of irritation from the breast immobilization system or the use of the medical adhesive spray during radiation treatment. The cup and flange will also be visually checked for any apparent effects.

At the time of conventional radiotherapy simulation, it will be determined whether or not the patient is an eligible candidate for GammaPod boost treatment. Whether or not the patient receives GammaPod treatment, her whole breast irradiation will start up to 7-8 days after the day of conventional radiotherapy simulation. This time is needed for physician contours, treatment planning by our dosimetry team, physician plan approval and physics plan approval (typically 4 working days) and also allowing for standard practice of beginning a course of whole breast irradiation on a Monday. This timeline is purely a function of workflow rather than clinical/radiobiological considerations. The CT images acquired with the patient in the supine position during simulation will be used for treatment planning. Whole breast treatments are devised according to our departmental guidelines. GammaPod patients will return on a single day prior to their conventional treatment to be CT scanned in the prone orientation and treated with GammaPod. It is possible that GammaPod simulation and treatment will be on the same day as conventional radiotherapy simulation, depending on schedules and patient availability. The timing of GammaPod boost treatment relative to conventional radiotherapy whole breast treatment does not affect the whole breast radiotherapy dose prescription. This is consistent with current clinical practice concerning boost dose delivery, whether pre (i.e. intraoperative radiotherapy) or post (i.e. external beam radiotherapy or brachytherapy) whole breast radiotherapy. Beginning on the day of GammaPod treatment, patients will be evaluated weekly for acute toxicities, as is our clinic's standard practice.

2. Objectives

The primary study objective is to demonstrate the feasibility and safety of delivering a tumor bed boost dose using the GammaPod™ stereotactic system for patients undergoing breast conserving therapy. Efficacy is not among the objectives of this study.

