5.4.3. Criteria for judging deviations from plan

- No deviation (acceptable): 100% prescription isodose surface covers at least 95% of the PTV. Maximum dose to the PTV should not exceed prescription dose by >20%. Minimum dose to the PTV should not be lower than 7.6Gy (below the prescription dose by 5%). All specified critical normal tissue DVH limits as described in 5.4.3 have been met. As compared with TB boosts with FDA approved brachytherapy techniques and intraoperative treatments, which are associated with dose “hot spots” of 100% - 400%, a 20% dose inhomogeneity within the TB PTV should be acceptable.
- Minor deviation but acceptable: 95% prescription isodose surface covers between 95% and 100% of the PTV. No portion of the PTV receives <93% of the prescription dose. Maximum dose to PTV exceeds prescription dose by >20% but <30%. All specified critical normal tissue DVH limits fall within 5% of the guidelines.
- Major deviations (unacceptable): 95% isodose surface covers < 95% of the PTV. A portion of PTV receives < 93% of prescription isocenter dose. Maximum dose to PTV exceeds prescription dose by >30%. Any critical normal tissue DVH limit exceeds 5% of the specified value.
- If a major deviation is required for treatment delivery, then the Gamma Pod treatment will not be delivered and the patient will be taken off study.

- Treatment delivery will not be performed if the seal of the breast cup is lost or pressure falls below a pre-determined value following the CT simulation. Such an event will be recorded.
- If the cup pressure drops to below 100 mmHg, which is signified by an alarm on the pump, the physician will do the following:
 - If it occurs before the simulation CT scan, continuation with the study should proceed once pressure is reestablished.
 - If pressure loss occurs following the simulation CT scan and before treatment, the CT simulation will need to be repeated to ensure the reproducibility of target position between CT scanning and treatment. The event will be recorded and the treating physician will decide whether to proceed with GammaPod treatment or treat the patient conventionally off study.
- Treatment delivery will not be performed if the breast cup cannot be locked into the treatment table. Such an event will be recorded.
- Treatment delivery will not be performed if the patient feels uncomfortable following the placement of the breast cup. Such an event will be recorded.

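### Section 1.3 lets a GammaPod plan with a PTV minimum between 7.2 and 7.44 Gy be approved, while section 5.4.3 forbids delivering it

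*Combined protocol and SAP*

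**What the plan says.** Section 1.3 (Schema/procedure) places an approval step before delivery: "The treatment plan will be reviewed and approved by the prescribing physician and physicist before being sent to the GammaPod system for delivery". Its criteria follow at once.

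- Coverage: "For a plan to be acceptable, the 8Gy isodose line must cover 95% of the PTV".
- Skin, for the same isodose line: "and must be at least 5mm from the breast skin surface".
- Minimum: "The minimum PTV dose must be greater than 7.2Gy, i.e., a maximum of 10% cold spot is allowed", on condition that 95% of the PTV receives at least 8 Gy.
- Maximum: "The maximum PTV dose must be less than 9.6Gy, i.e., a maximum of 20% hot spot is allowed".

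Section 5.4.3 (Criteria for judging deviations from plan) grades the same plan in three tiers.

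- No deviation: the 100% isodose covers at least 95% of the PTV, the maximum is no more than 20% above prescription, and "Minimum dose to the PTV should not be lower than 7.6Gy".
- Minor, still acceptable: the 95% isodose covers 95% to 100% of the PTV, no part is below 93%, and "Maximum dose to PTV exceeds prescription dose by >20% but <30" (per cent).
- Major, unacceptable: among other triggers, "A portion of PTV receives < 93% of prescription isocenter dose". A plan that needs a major deviation is not delivered and the patient leaves the study.

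Section 10.1 names 5.4.3 as the scoring standard for the primary feasibility endpoint. Section 10.2 and the list of objectives in section 1.2 name 5.5.4 instead, which holds dose-volume criteria for whole-breast irradiation.

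**The concern.** Both sections bear on whether the boost is given, and they do not set the same lower limit. The 7.2 Gy figure in 1.3 matches neither the 7.6 Gy of the no-deviation tier nor the 7.44 Gy floor for delivery. Staff who approve by 1.3 could send forward a plan that 5.4.3 says must not be delivered.

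Plan acceptability is also what the two-stage design counts. A plan approved by 1.3 and scored by 5.4.3 could be delivered and then counted as unacceptable, although section 10.2 says that a plan graded unacceptable is aborted. This is a first-in-human device study, and the decision is made while the patient wears the vacuum cup, with less than 75 minutes expected from cup placement to the end of treatment. The rule should be settled in advance.

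**Working it through.** **1. The plan's own design figures.** Inputs from section 10.2: stop if 5 or fewer of 8 plans are acceptable; reject the device if 13 or fewer of 17 are; p0 = 0.60, p1 = 0.90.

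- Early stop = P(Bin(8, p) ≤ 5). At p = 0.60 this is 0.685 (stated: 68%).
- Expected N = 8 + 9 × (1 − 0.6846) = 10.84 (stated: 10.8).
- P(device accepted) = Σ over x = 6 to 8 of P(Bin(8, p) = x) × P(Bin(9, p) ≥ 14 − x). This is 0.0436 at 0.60 (stated: 4.4%) and 0.9045 at 0.90 (stated: 90.5%).

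All four reproduce.

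**2. Limits in Gy for the 8 Gy prescription (5.4.1).** 90% = 7.20; 93% = 7.44; 95% = 7.60; 120% = 9.60; 130% = 10.40.

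| Limit | 1.3 approval | 5.4.3 no deviation | 5.4.3 minor |
|---|---|---|---|
| PTV minimum | > 7.2 | ≥ 7.6 | ≥ 7.44 |
| PTV maximum | < 9.6 | ≤ 9.6 | above 9.6, below 10.4 |
| Coverage | 8 Gy to 95% | 8 Gy to ≥ 95% | 7.6 Gy to 95–100% |

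On maximum and coverage, 1.3 equals the no-deviation tier apart from the exact 9.6 Gy boundary. On the minimum it matches no tier and lies below the floor for delivery.

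**3. Example plans.** The values are assumed, and the normal-tissue and skin rules are taken as met. V100 and V95 are the percentages of the PTV receiving at least 8 Gy and 7.6 Gy.

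| Plan | V100 | V95 | Min (Gy) | Max (Gy) | 1.3 | 5.4.3 |
|---|---|---|---|---|---|---|
| A | 96 | 97 | 7.3 | 9.0 | passes | major, not delivered |
| B | 96 | 100 | 7.7 | 10.0 | fails maximum | minor, deliverable |
| C | 90 | 98 | 7.5 | 9.0 | fails coverage | minor, deliverable |
| D | 96 | 98 | 7.5 | 9.0 | passes | minor, deliverable |

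Plan A is the contradiction. Plans B and C show the secondary tension. Plan D is deliverable under both sections.

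**4. Size of the minimum band.** Width: 7.44 − 7.20 = 0.24 Gy. With the formula and α/β of 3 to 4 from section 1.2, BED = D(1 + D/(α/β)) for one fraction, and the equivalent in 2 Gy fractions is EQD2 = BED/(1 + 2/(α/β)).

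- α/β = 4: 7.2 Gy gives 20.16/1.5 = 13.44 Gy, and 7.44 Gy gives 14.19 Gy, a difference of 0.75 Gy. The prescription gives 16.0 Gy.
- α/β = 3: 14.69 and 15.53 Gy, a difference of about 0.85 Gy. The prescription gives 17.6 Gy.

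Because 1.3 requires 8 Gy to 95% of the PTV, the cold region is at most 5% of it. For the 5 cm and 3 cm spheres mentioned in 1.3 that is 0.05 × 65.45 = 3.27 cc and 0.05 × 14.14 = 0.71 cc.

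**5. Size of the maximum band.** 10.4 − 9.6 = 0.8 Gy, or 3.2 Gy (α/β = 4) to 3.7 Gy (α/β = 3) in EQD2, as a point maximum.

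**The case against.** The best reply is that the governing text can be inferred. Section 1.3 outlines the general sequence, while section 5 is the radiation protocol. Section 10.1 names 5.4.3 for scoring, and the three-tier wording in 10.2 fits only 5.4.3 despite the wrong number. Section 5.4.3 also carries an express stop, so delivering plan A means overlooking it. Much of this stands. It makes an error less likely, but it does not remove a mandatory approval criterion that permits what the stop forbids.

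Several stronger readings are tempting, and the documents do not support them.

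- *Minimum, maximum and coverage are all in outright conflict.* Only the minimum cannot be reconciled. On the other two, 1.3 states the no-deviation values, and a minor tier exists to tolerate missing them. What remains is that 1.3 words these values as conditions of acceptability.
- *Section 1.3 would turn patients away.* It has no off-study rule. Removal from GammaPod treatment on dosimetric grounds follows from a major deviation (5.4.3) or an unacceptable grade (10.2). Optimization takes under 2 minutes, so a failing plan can be re-optimized first.
- *The 5 mm skin rule is inconsistent.* It is stated once and contradicted nowhere. Section 5.3.2 limits the PTV contour, 5.4.2 limits surface dose, and 3.2 excludes a tumor bed within 5 mm of skin. None of these replaces the isodose rule, so it should survive the edit.
- *The maximum band is a demonstrated safety problem.* The remark in 1.2 about side effects at higher doses supports choosing 8 Gy over 9–10 or 20 Gy. It does not address a point maximum of 9.6 versus 10.4 Gy. Sections 1.3 and 5.4.3 both compare the plan with much larger hot spots in other techniques, and 1.3 says those were not linked to poor cosmesis.

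**Conclusion.** The contradiction on the minimum PTV dose is real. A plan with a minimum above 7.2 and below 7.44 Gy meets the section 1.3 minimum and must not be delivered under 5.4.3. The mandatory wording of the 1.3 maximum and coverage limits is a lesser ambiguity, and the reference to 5.5.4 in 10.2 is a wrong section number that bears on the primary endpoint.

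The size is small: 0.24 Gy in at most 5% of the PTV. The documents do not give the share of plans in the band. If no plan falls there, the effect is nil. The endpoint count is affected only if plans are approved or scored by 1.3 instead of by 5.4.3 as section 10.1 directs.

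A reader might infer that the two-stage design is undermined. It is not: its figures reproduce, and they do not depend on which limits define an acceptable plan. The EQD2 figures rest on the protocol's own formula and α/β range. Severity is minor, but the rule should be corrected before enrolment because it decides delivery.

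**What to change.** 1. State in 5.4.3 that it is the single set of limits for approval, delivery and endpoint scoring.
2. In 1.3, replace the 7.2 Gy minimum with a reference to 5.4.3: 7.6 Gy for no deviation, 7.44 Gy as the floor for delivery.
3. Say in 1.3 that its 9.6 Gy maximum and its 8 Gy coverage of 95% of the PTV are the no-deviation targets, and that 5.4.3 sets the tolerance.
4. Carry the rule keeping the 8 Gy line at least 5 mm from the skin into 5.4.2, so that it is not lost.
5. Change 5.5.4 to 5.4.3 in sections 1.2 and 10.2.

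The cost is protocol wording only. No patients or procedures are added, and the sample size, stopping boundaries and error rates stay as they are.
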